5.1 Disposition

The following will be summarized for the enrolled population, by treatment group and overall for all participants:

- The number of participants who were randomized in each cohort
- The number of participants who received each treatment
- The number of participants who completed the study
- The number of participants who did not complete the study (both overall and according to reasons for study withdrawal)

- The number of participants who were unblinded by the site
- The number of participants in each analysis population
- The number of participants who screen failed (both overall and according to reasons for screen failure)

Participant disposition and screen failure data will be presented in data listings.

5.2 Protocol Deviations

Significant protocol deviations will be summarized by treatment group. All protocol deviations will be presented in a data listing. Protocol deviations will be maintained in an Excel spreadsheet, which will include the deviation description, date of deviation, deviation category, and significance (significant/not significant). The protocol deviation spreadsheet will be finalized prior to database lock.

5.3 Inclusion and Exclusion Criteria

Inclusion and exclusion criteria deviations will be presented in a data listing.

6. Demographics and Baseline Characteristics

6.1 Demographics

Demographic and other baseline information collected at screening will be presented in a data listing. Descriptive statistics will be calculated for the following continuous demographic and other baseline characteristics:

- Age (years)
- Weight (kg)
- Height (cm)
- Body mass index (BMI) (kg/m²)
- Pulse rate (beats/minute)
- Systolic blood pressure (SBP) (mmHg)
- Diastolic blood pressure (DBP) (mmHg)
- Temperature (C)
- Oxygen saturation (%)

Frequency counts and percentages will be tabulated for the categorical variables:

- Sex
- Race
- Ethnicity

The summaries will be presented by treatment group and overall for the safety population.

6.2 Medical History

The medical history data will be coded using the Medical Dictionary for Regulatory Activities (MedDRA, version to be delineated in the clinical study report [CSR]) and summarized by treatment group. All medical history data will be presented in a data listing.

7. Treatments and Medications

7.1 Prior and Concomitant Medications

Medications that are discontinued prior to study intervention administration will be classified as prior medication. Medications for which dosing is begun on or after study intervention administration will be classified as concomitant. If a medication is begun before study intervention administration and is discontinued on or after study intervention administration, then the medication will be classified as both prior and concomitant.

All prior and concomitant medications will be coded according to the World Health Organization Drug Dictionary (version to be delineated in the CSR) and presented in a data listing.

7.2 Study Treatment

The study drug administration as collected on eCRF will be presented in the data listings.

8. Pharmacokinetics

8.1. Pharmacokinetic Concentrations

Whole blood samples on VAMS and serum samples will be collected for measurement of RSM01 concentrations in capillary blood and venous serum as below:

Dose Escalation Phase:

- At Visit 1 (Day 1), PK blood draw will occur pre-dosing, within 5 minutes (\pm 1 minute) after end of infusion for IV dosing only, and at 8-hours (\pm 0.5 hours) post-dose for both IV and IM doses.
- Visit 2 (Day 2): 24-hours (\pm 1 hours)
- Visit 3 (Day 3): (\pm 0 day)
- Visit 4 (Day 6): (\pm 1 day)
- Visit 5 (Day 8): Days 8-10
- Visit 6 (Day 15): (\pm 3 days)
- Visit 7 (Day 29): Days 29-35
- Visit 8 (Day 61): (\pm 7 days)
- Visit 9 (Day 91): (\pm 7 days)
- Visit 10 (Day 121): (\pm 7 days)
- Visit 11 (Day 151): (\pm 7 days)
- Discontinuation visit

Dose Expansion Phase:

- At Visit 1 (Day 1): pre-dose

- Visit 2 (Day 8): Days 8-10
- Visit 3 (Day 29): Days 29-35
- Visit 4 (Day 91): (\pm 7 days)
- Visit 5 (Day 151): (\pm 7 days)
- Discontinuation visit

Individual capillary blood concentration of RSM01 and time deviation data for PK population will be presented in data listings. Capillary blood concentration data will be summarized by scheduled time point for the PP population using descriptive statistics (non-missing observations (N), arithmetic mean (Mean), standard deviation (SD), coefficient of variation (CV%), median, minimum, maximum, Q1 and Q3. Capillary blood concentration data will also be summarized by ADA status using the PK population.

Descriptive statistics of capillary blood concentration of RSM01 data will be calculated using values with the same precision as the source data and rounded for reporting purposes only. The following conventions will be applied when reporting descriptive statistics of PP PK concentration data:

- Mean, Min, Median, Max, Q1, Q3: 3 significant digits
- SD: 4 significant digits
- CV%: 1 decimal place

Concentrations of RSM01 that are below the lower limit of quantification (BLQ) before the first quantifiable concentration will be treated as zero for descriptive statistics. Below the limit of quantification values after the first quantifiable concentration will be set as missing and excluded for summary statistics.

Mean (\pm SD) capillary blood concentrations of RSM01 versus scheduled time profiles will be plotted by treatment on both linear and semi-logarithmic scales for PK population. Individual capillary blood concentrations versus actual time profiles will be plotted on both linear and semi-logarithmic scales for the PP population. The ADA status for each subject will be displayed on the individual profiles and for ADA positive participants, the titer results will be plotted on the secondary Y-axis.

The same analyses will be performed for venous serum (exploratory objective).

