**Table 7: Summary of Primary and Secondary Endpoints and Analyses**

Endpoint	Statistical Analysis
Primary:	
Unsolicited AEs through Day 151	The incidence and Clopper-Pearson 95% CIs of AEs and SAEs/AESIs will be summarized by treatment group, dose levels, routes of administration and overall, and by intensity.
All SAEs/AESIs through Day 151	Duration, day of onset of local and systemic solicited AEs will be summarized by group. Relationship of unsolicited AEs and SAEs/AESIs to the study intervention will be summarized by group.
Solicited systemic AEs through Day 7	Any infusion reactions will be described.
Solicited local AEs for injection site reactions for 7 days after dose administration (only applies to IM doses)	
Secondary:	
Safety laboratory parameters Grade 1 and above through Day 151	The incidence of safety parameters outside of normal ranges (Grade 1 and above), change from baseline, grades, grade shifts, as applicable, will be summarized by treatment group, dose levels, routes of administration and overall, and by intensity, and relationship to the study intervention.
PK parameters  AUC 0-∞ , CD 91 , AUC 0-D91 , CD 151 , AUC 0-D151 C max , C min , T max , t 1/2 , CL and V Z	RSM01 capillary blood concentrations and PK parameters will be summarized by treatment group using descriptive statistics, and the number of participants. Following summaries will be provided arithmetic mean, standard deviation, arithmetic percent CV, median, minimum, maximum, geometric mean, and geometric percent CV.  The proportion of participants with observed or predicted CD 151 concentrations above the EC 90 will be summarized by treatment group and country, as appropriate.
Incidence of ADAs to RSM01 through Day 151	ADA incidence will be summarized by treatment group. Exact analyses will be pre-specified in the SAP.

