8.2. Pharmacokinetic Parameters

Individual capillary blood concentration of RSM01 versus actual time data will be used to estimate the PK parameters of RSM01 by standard noncompartmental methods using WinNonlin (Phoenix) version 8.0 or higher. For the calculation of PK parameters, BLQ values before the first quantifiable concentration of RSM01 will be treated as zero. Below the limit of quantification values after the first quantifiable concentration will be set as missing. Missing concentrations will be treated as missing. If consecutive BLQ concentrations of RSM01 are

followed by quantifiable concentrations in the terminal phase, those concentrations after BLQ concentrations will be treated as missing.

The following PK parameters for capillary blood RSM01 will be calculated for dose escalation cohorts and dose expansion cohort, if data permit.

Parameter	Description
C_{\max}	Maximum observed capillary blood concentration of RSM01
C_{\min}	Minimum observed capillary blood concentration of RSM01
C_{D91}	Day 91 capillary blood concentration of RSM01
C_{D151}	Day 151 capillary blood concentration of RSM01
T_{\max}	Time to reach maximum observed capillary blood concentration of RSM01
$AUC_{0-\infty}$	Area under the capillary blood concentration curve for RSM01 from time 0 to the infinity, calculated using the linear trapezoidal linear interpolation method
AUC_{0-D91}	Area under the capillary blood concentration curve for RSM01 from time 0 to Day 91, calculated using the linear trapezoidal linear interpolation method
AUC_{0-D151}	Area under the capillary blood concentration curve for RSM01 from time 0 to Day 151, calculated using the linear trapezoidal linear interpolation method
CL	Total body clearance (for IV); calculated as Dose/ $AUC_{0-\infty}$
CL/F	Apparent total body clearance (for IM); calculated as Dose/ $AUC_{0-\infty}$
V_z	Volume of distribution (for IV); calculated as Dose/($AUC_{0-\infty} \times \lambda_z$)
V_z/F	Apparent volume of distribution (for IM); calculated as Dose/($AUC_{0-\infty} \times \lambda_z$)
$t_{1/2}$	Apparent terminal half-life; calculated as $0.693/\lambda_z$

The following PK parameters will be calculated for diagnostic purposes and listed, but they will not be summarized.

Parameter	Description

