8.3. Statistical analysis

Dose proportionality for capillary blood RSM01 PK parameters will be tested using the power regression model for AUC_{0-inf} , AUC_{0-D91} , AUC_{0-D151} , and C_{max} and, defined as:

$$\ln [\text{PK parameter}] = \beta_0 + \beta_1 \ln [\text{Dose}]$$

where the PK parameter is an AUC_{0-inf} , AUC_{0-D91} , AUC_{0-D151} , and C_{max} . The null hypothesis being tested is that the AUC and C_{max} values are dose proportional, or slope (β_1) = 1. Dose-proportionality will be concluded if the 90% CI of the slope β_1 lies entirely within $[1+\ln(0.5)/\ln(r), 1+\ln(2.0)/\ln(r)]$, where r is a ratio that describes the dose range and is defined as the ratio of highest dose/lowest dose.

Bioavailability of RSM01 following IM injection will be calculated using the ratio of geometric mean of $AUC_{0-\infty}$ and AUC_{0-D151} capillary blood RSM01 PK parameters for the comparison of IM versus IV dose. Log-transformed $AUC_{0-\infty}$ and AUC_{0-D151} estimates will be analyzed using an analysis of variance (ANOVA) model with treatment group as a factor. The parameter estimates results will be exponentiated and the ratio of geometric means and 90% CIs will be presented.

The proportion of participants with observed C_{D151} concentrations above the estimated EC90 for RSM01 (based on available pre-clinical data) will be summarized by treatment group. Exact 95% confidence interval will be calculated on the percentages.

The same analyses will be performed for venous serum (exploratory objective).

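### Late BLQ concentrations are set to missing, so any BLQ result at Day 91 or Day 151 drops out of the summaries, and the undefined EC90 denominator may lose it too; any resulting bias is upward

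*SAP*

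**What the plan says.** SAP 8.1 has two rules for the concentration tables. BLQ values "before the first quantifiable concentration will be treated as zero for descriptive statistics"; for later ones, "Below the limit of quantification values after the first quantifiable concentration will be set as missing and excluded for summary statistics". SAP 8.2 repeats the second rule for parameter calculation: "Below the limit of quantification values after the first quantifiable concentration will be set as missing". The parameter list in that section includes C_D91 and C_D151, the latter defined as "Day 151 capillary blood concentration of RSM01".

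SAP 8.3 then plans a binary summary with an exact 95% interval: "The proportion of participants with observed C_{D151} concentrations above the estimated EC90 for RSM01 (based on available pre-clinical data"). It does not name a denominator or say how a BLQ Day 151 result is classified. Protocol 9.3.4 also refers to observed values, while Protocol Table 7 reads "The proportion of participants with observed or predicted" C_D151 concentrations.

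SAP 8.1 adds a table by anti-drug antibody status: "Capillary blood concentration data will also be summarized by ADA status using the PK population". The N in the concentration tables is the count of non-missing observations. No BLQ count per visit, BLQ sensitivity analysis or LLOQ appears in either document.

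**The concern.** A late BLQ result is a measurement. It says that the concentration is below a known limit. The rule treats it like a missed visit and removes only the lowest values. The mean, geometric mean, median and minimum of what remains can therefore only move up.

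For the EC90 summary the information is complete whenever the LLOQ is below EC90, because a BLQ result is then a known negative. If C_D151 becomes missing under 8.2 and 8.3 counts participants with an observed C_D151, a programmer following the text would drop that participant from numerator and denominator alike. Day 151 concentration above EC90 is the efficacy threshold that the Protocol uses in its dose rationale (2.5.1, 2.5.2, 4.1). The rule would do most harm if RSM01 cleared faster than expected, a possibility that Protocol 2.5.2 itself allows for.

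**Working it through.** **Inputs from the documents.** RSM01 arm sizes: 6 per escalation cohort and 24 in Cohort 5 (SAP 4.2, 4.3). EC90: 6.8 µg/mL, reported for nirsevimab, with RSM01 described as similar (Protocol 2.5.1). Predicted Day 151 exposure: above EC90 at 300 mg and over (Protocol 2.5.1).

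**Assumptions.** LLOQ 1 to 5 µg/mL; Day 151 concentrations lognormal with CV 30–80%; the number of BLQ results.

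**The plan's own figure.** The only sample-size figure is the chance of seeing at least one AE, 1 − (1 − p)^n. With n=6 and p=23.53% it gives 80.0%; with n=24 and p=6.49%, 80.0%. This reproduces and confirms the arm sizes, but does not bear on the BLQ rule.

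**Step 1: EC90 proportion.** Let x participants of N be above EC90 and k be BLQ. Dropping BLQ gives x/(N − k); counting BLQ as not above gives x/N. The difference is xk / [N(N − k)]. Intervals are exact 95% (Clopper-Pearson).

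| N | Quantifiable but not above EC90 | k | BLQ dropped | BLQ counted as not above | Difference (points) |
|---|---|---|---|---|---|
| 24 | 0 | 1 | 23/23 = 100% (85.2–100) | 23/24 = 95.8% (78.9–99.9) | 4.2 |
| 24 | 2 | 1 | 21/23 = 91.3% (72.0–98.9) | 21/24 = 87.5% (67.6–97.3) | 3.8 |
| 24 | 4 | 1 | 19/23 = 82.6% (61.2–95.0) | 19/24 = 79.2% (57.8–92.9) | 3.4 |
| 24 | 2 | 4 | 18/20 = 90.0% (68.3–98.8) | 18/24 = 75.0% (53.3–90.2) | 15.0 |
| 6 | 0 | 1 | 5/5 = 100% (47.8–100) | 5/6 = 83.3% (35.9–99.6) | 16.7 |
| 6 | 1 | 1 | 4/5 = 80.0% (28.4–99.5) | 4/6 = 66.7% (22.3–95.7) | 13.3 |

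With k = 0 the two columns agree.

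**Step 2: how likely is a late BLQ?** With geometric mean GM and s = √ln(1 + CV²), P(BLQ) = Φ[ln(LLOQ/GM)/s]. The true share above EC90 is 1 − Φ[ln(6.8/GM)/s]. The share reported with BLQ dropped is the true share divided by 1 − P(BLQ).

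| Assumed Day 151 GM (µg/mL) | Assumed LLOQ (µg/mL) | P(BLQ) | Rise in EC90 proportion (points) | Rise in geometric mean |
|---|---|---|---|---|
| 10–15 | 1 | at most 0.05% | essentially 0 | essentially 0 |
| 10–15 | 3 | 0–4.4% | 0–3.2 | up to 7% |
| 10–15 | 5 | up to 16% | 0–13.7 | up to 23% |
| 3, CV 80% | 1 | 5.9% | 0.8 | 9% |
| 3 | 3 | 50% | 0.3–12.2 (the proportion doubles) | 26–75% |

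Worked case: GM 10, CV 80%, LLOQ 5. P(BLQ) = 16.2% and the true share above EC90 is 70.8%. The reported share is 70.8/(1 − 0.162) = 84.5%, a rise of 13.7 points.

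**The case against.** **The EC90 denominator.** SAP 8.3 defines none. The word observed may serve only to contrast with predicted, as in Protocol Table 7; on that reading a BLQ participant stays in as not above. A reader might infer that the plan certainly drops these participants. The documents do not establish that. What stands is that two defensible readings give different answers and nothing chooses between them. The loss from the concentration, C_D91 and C_D151 summaries does not depend on this ambiguity, because 8.1 and 8.2 state it directly.

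**Whether it will happen.** With exposure as predicted and an LLOQ of 1 µg/mL or less, Step 2 finds essentially no effect. This stands: the bias is conditional.

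**Anti-drug antibodies.** It is tempting to argue that the rule hides an antibody effect on exposure. The evidence in Protocol 2.6 is weak for this: lower exposure was seen between days 150 and 360 in some infants given nirsevimab, and almost all positive results came after day 150. In adults given nirsevimab, post-dose antibody rates were similar on active and placebo (13.7% and 15.2%). The SAP also lists individual concentrations and marks antibody status and titre on individual profiles, so attrition would be partly visible. Even so, the summary tables could not separate BLQ from a missed sample.

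**Importance.** Safety is primary, the trial is descriptive, and the EC90 proportion is an analysis under a secondary PK objective. The model-based Day 151 predictions informing Cohort 5 dose selection, and the infant dose predictions, come from population PK modelling (Protocol 2.5.2, 9.3.4). Calling this the key PK result, or saying that it decides the dose, goes beyond the documents.

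**Conclusion.** The point holds in conditional form. If any Day 91 or Day 151 sample is BLQ, the stated rules remove it from the concentration and C_D91/C_D151 summaries. On the natural but not the only reading of SAP 8.3, a Day 151 BLQ result also leaves the EC90 proportion. Any bias is upward: 3.4 to 4.2 points for one BLQ participant in the N=24 examples, and 13.3 to 16.7 points for one at N=6. It is zero without late BLQ results, and likely small if the LLOQ is well below 6.8 µg/mL and exposure is as predicted.

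These sizes rest on assumed BLQ counts and, in Step 2, on an assumed LLOQ, CV and geometric mean. Counting BLQ as not above also requires an LLOQ below EC90. A reader might infer that the Day 151 result is already biased; the documents support only that it would be if late BLQ results occur. This is a should-fix, best settled before unblinding so that the denominator is not chosen with the data in view.

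**What to change.** - **SAP 8.3:** define the denominator of the EC90 proportion as all participants in the named analysis population with an assayed Day 151 sample. Count a BLQ result as not above EC90, provided the LLOQ is below EC90.
- **SAP 8.1:** state the LLOQ and report the number BLQ at each visit, including in the table by anti-drug antibody status.
- **Sensitivity summary:** add one for concentrations, C_D91, C_D151 and C_min that retains BLQ values, for example at LLOQ/2 or through a censored-data geometric mean. Neither need replace the main summary, since LLOQ/2 is one convention among several.
- **SAP 8.2:** keep late BLQ as missing for λz and AUC in the noncompartmental analysis.

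The cost is a few sentences in the SAP, one programming rule and one extra summary. No new data are needed, and the estimates do not change if no late BLQ occurs.

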8.2. Pharmacokinetic Parameters

Individual capillary blood concentration of RSM01 versus actual time data will be used to estimate the PK parameters of RSM01 by standard noncompartmental methods using WinNonlin (Phoenix) version 8.0 or higher. For the calculation of PK parameters, BLQ values before the first quantifiable concentration of RSM01 will be treated as zero. Below the limit of quantification values after the first quantifiable concentration will be set as missing. Missing concentrations will be treated as missing. If consecutive BLQ concentrations of RSM01 are

followed by quantifiable concentrations in the terminal phase, those concentrations after BLQ concentrations will be treated as missing.

The following PK parameters for capillary blood RSM01 will be calculated for dose escalation cohorts and dose expansion cohort, if data permit.

Parameter	Description
C_{\max}	Maximum observed capillary blood concentration of RSM01
C_{\min}	Minimum observed capillary blood concentration of RSM01
C_{D91}	Day 91 capillary blood concentration of RSM01
C_{D151}	Day 151 capillary blood concentration of RSM01
T_{\max}	Time to reach maximum observed capillary blood concentration of RSM01
$AUC_{0-\infty}$	Area under the capillary blood concentration curve for RSM01 from time 0 to the infinity, calculated using the linear trapezoidal linear interpolation method
AUC_{0-D91}	Area under the capillary blood concentration curve for RSM01 from time 0 to Day 91, calculated using the linear trapezoidal linear interpolation method
AUC_{0-D151}	Area under the capillary blood concentration curve for RSM01 from time 0 to Day 151, calculated using the linear trapezoidal linear interpolation method
CL	Total body clearance (for IV); calculated as Dose/ $AUC_{0-\infty}$
CL/F	Apparent total body clearance (for IM); calculated as Dose/ $AUC_{0-\infty}$
V_z	Volume of distribution (for IV); calculated as Dose/($AUC_{0-\infty} \times \lambda_z$)
V_z/F	Apparent volume of distribution (for IM); calculated as Dose/($AUC_{0-\infty} \times \lambda_z$)
$t_{1/2}$	Apparent terminal half-life; calculated as $0.693/\lambda_z$

The following PK parameters will be calculated for diagnostic purposes and listed, but they will not be summarized.

Parameter	Description
λ_z	Elimination rate constant, calculated by linear regression of the terminal portion of the natural log capillary blood concentration versus time curve. Visual assessment may be used to identify the terminal linear phase of the natural log capillary blood concentration versus time profile. A minimum of 3 data points (excluding C_{max} for IM) will be used for calculation. The parameter λ_z will not be calculated if the terminal phase of the natural log capillary blood concentration versus time profile does not exhibit a linear decline phase or if the $Rsq < 0.8$
λ_z lower	Lower limit of time included in the calculation of λ_z
λ_z upper	Upper limit of time included in the calculation of λ_z
λ_z N	Number of data points used in the calculation of λ_z
Rsq	Regression coefficient for calculation of λ_z .

Additional PK parameters may be calculated. Individual capillary blood RSM01 PK parameters will be presented in the data listings for the PP population. The capillary blood RSM01 PK parameters will be summarized using the PP population by treatment with the following descriptive statistics: N, n, mean, SD, CV, median, minimum, maximum, geometric mean, and geometric percent CV.

Capillary blood PK parameters for RSM01 will be displayed to 3 significant figures in all data listings and summary tables, with exception of time variables (T_{max} , λ_z lower, and λ_z upper) which will be displayed to 2 decimal places. λ_z which will be displayed to 4 decimal places.

Scatter plots of capillary blood RSM01 PK parameters (AUC_{0-inf} , AUC_{0-D91} , AUC_{0-D151} , and C_{max}) vs. IV dose will be plotted with an equation and R^2 value.

The same analyses will be performed for venous serum (exploratory objective).

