### 3. Objectives and Endpoints

**Table 4: Objectives and Endpoints**

Objectives	Endpoints (Endpoints apply to all cohorts unless noted)
Primary	
To characterize the safety and tolerability of a single dose of RSM01	
 
Unsolicited AEs through Day 151
 
All serious adverse events (SAEs) and AESIs through Day 151
 
Solicited systemic AEs for 7 days after dose administration
 
Solicited local AEs for injection site reactions for 7 days after dose administration (only applies to IM doses)
 

Secondary	
To characterize safety laboratory parameters following RSM01 administration	
 
Safety laboratory parameters Grade 1 and above through Day 151
 

To characterize the pharmacokinetics (PK) following RSM01 administration	
PK parameters including:
 
 
Area under the capillary blood-concentration time curve from zero to infinity (<math>AUC_{0-\infty}</math>)
 
Day 91 capillary blood-concentration and area under the capillary blood-concentration time curve (<math>C_{D91}</math> and <math>AUC_{0-D91}</math>)
 
Day 151 capillary blood-concentration and area under the capillary blood-concentration time curve (<math>C_{D151}</math> and <math>AUC_{0-D151}</math>)
 
<math>C_{max}</math> following IM administration and <math>C_0</math> following IV administration), <math>C_{min}</math>
 
<math>T_{max}</math> and <math>t_{1/2}</math>
 
CL
 
<math>V_z</math> of RSM01 through Day 151
 

To characterize the formation of ADAs following RSM01 administration	
 
Incidence of ADAs to RSM01 through Day 151
 

Exploratory	
To characterize RSV neutralizing antibody activity following RSM01 administration	

• Capillary blood RSV neutralizing antibody levels through Day 151

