2.2 Secondary Objectives and Endpoints

Secondary objectives	Endpoint description

• To characterize safety laboratory parameters following RSM01 administration	
• Safety laboratory parameters through Day 151

• To characterize the pharmacokinetics (PK) following RSM01 administration	
PK parameters including:
 
• Area under the capillary blood-concentration time curve from zero to infinity ($AUC_{0-\infty}$)• Day 91 concentration and area under the capillary blood-concentration time curve (C_{D91} and AUC_{0-D91})• Day 151 concentration and area under the capillary blood-concentration time curve (C_{D151} and AUC_{0-D151})• Maximum capillary blood-concentration (C_{max} following IM administration and C_0 following IV administration)• Minimum concentration (C_{min})• Time to maximum capillary blood-concentration (T_{max}) and apparent terminal half-life ($t_{1/2}$)• Systemic clearance (CL for IV or CL/F for IM)• Volume of distribution of RSM01 (V_z for IV or V_z/F for IM) through Day 151

• To characterize the formation of anti-drug antibodies (ADAs) following RSM01 administration	
• Incidence of ADAs to RSM01 through Day 151

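### SAP 8.2 defines C_min without excluding the pre-dose sample, so its BLQ-to-zero rule makes C_min equal 0 for any participant whose pre-dose sample is BLQ

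*SAP*

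**What the plan says.** Minimum concentration is listed among the secondary PK endpoints in Protocol Table 4 and SAP 2.2. The parent objective in the protocol is "To characterize the pharmacokinetics (PK) following RSM01 administration".

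The SAP 8.2 parameter table describes C_min as "Minimum observed capillary blood concentration of RSM01". It gives no time window and does not limit the definition to post-dose samples.

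SAP 8.2 also fixes the BLQ handling. Its first rule is "For the calculation of PK parameters, BLQ values before the first quantifiable concentration of RSM01 will be treated as zero". Its second is "Below the limit of quantification values after the first quantifiable concentration will be set as missing". Neither rule makes an exception for C_min.

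SAP 8.1 schedules a pre-dose sample in both phases: "At Visit 1 (Day 1), PK blood draw will occur pre-dosing" for Cohorts 1 to 4, and "At Visit 1 (Day 1): pre-dose" for Cohort 5.

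SAP 8.2 summarises PK parameters by treatment in the PP population. The statistics include mean, SD, CV, geometric mean and geometric percent CV. The same analyses are planned for venous serum as an exploratory item.

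**The concern.** Each rule is ordinary on its own. A zero at time 0 is a usual starting point for an IM AUC, and a minimum observed value is a usual descriptor. Applied together, they turn C_min into a report of the sample taken before the drug was given, although the objective is PK after administration.

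At stake is one listed secondary endpoint that would carry no information. Some of its planned summary statistics would not exist, and a decision on which samples count would have to be made after the data are in hand.

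**Working it through.** The documents give no numerical value for C_min, so there is no figure to reproduce. The check applies the SAP rules as written.

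**Step 1: the pre-dose value.** RSM01 is first-in-human (SAP 3). Protocol 5.2 excludes earlier dosing in this study (criterion 13) and antibody therapy within 180 days before Day 1 (criterion 10). The pre-dose sample is therefore expected to be BLQ. It comes before the first quantifiable value, so SAP 8.2 sets it to 0.

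**Step 2: the minimum.** C_min = min(0, c1, c2, ...) with every c ≥ 0, so C_min = 0. This does not depend on dose, route, half-life or absorption rate. A late BLQ value is set to missing, so it cannot supply the minimum.

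**Step 3: how many.** Planned RSM01 recipients are 4 × 6 + 24 = 48. If a share q of pre-dose samples were missing or quantifiable (q is an assumption), the number at zero is 48 × (1 − q):

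| q | Participants with C_min = 0 |
|---|---|
| 0 | 48 |
| 2% | 47.0 |
| 5% | 45.6 |
| 10% | 43.2 |

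**Step 4: the planned statistics.** In a group where all values are 0, mean = 0, SD = 0 and CV = 0/0, which is undefined. The geometric mean needs the mean of ln(C_min), and ln(0) is not finite. The geometric CV fails for the same reason. For the two geometric statistics a single zero in a group is enough, so the result for a cohort of 6 does not require that all 6 be zero.

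**Step 5: would limiting C_min to post-dose samples be enough?** In Cohorts 1, 3 and 4 (IV) and in Cohort 5 (first post-dose sample at Day 8), the post-dose minimum is normally the last quantifiable value. Cohort 2 (300 mg IM) is also sampled at 8 hours, during absorption. The documents give no human PK for RSM01, so what follows rests on assumed inputs: a two-compartment model with first-order absorption, V1 3.0 L, V2 2.3 L, Q 0.5 L/day, F 0.8, ka 0.2 to 0.5 per day, and clearance set to give the stated terminal half-life. Day 151 is 150 days after dosing.

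| Half-life (days) | 8 h, ka 0.2 to 0.5 (µg/mL) | Day 151 (µg/mL) | Which is lower |
|---|---|---|---|
| 20 | 5.0 to 11.8 | 0.2 to 0.3 | Day 151 at every ka |
| 40 | 5.0 to 11.9 | 3.2 to 3.4 | Day 151 at every ka |
| 50 | 5.0 to 11.9 | 5.5 to 5.7 | 8 h at ka 0.2 only |
| 60 | 5.0 to 11.9 | 7.8 to 8.1 | 8 h at ka 0.2 and 0.3 |
| 80 | 5.0 to 11.9 | 12.1 to 12.5 | 8 h at every ka |

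A separate one-compartment simulation (V 6 L, F 0.8, 20% between-subject variability, LLOQ 0.5 µg/mL, all assumed) points the same way. At a half-life of 60 days and an absorption half-life of 2 days, the Cohort 2 geometric mean is 4.27 µg/mL for the post-dose minimum and 6.71 µg/mL for C_D151. At a half-life of 30 days, the 8-hour sample is not the minimum.

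**Step 6: a window at or after T_max.** In the same one-compartment simulation, the minimum from T_max onward is the last quantifiable value in every cohort. That is C_D151 whenever Day 151 is quantifiable.

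**The case against.** **C_min drives nothing.** This stands. In SAP 8.3, dose proportionality uses the AUCs and C_max, bioavailability uses AUC to infinity and AUC to Day 151, and the EC90 proportion uses C_D151. Cohort 5 dose selection rests on population PK predictions (Protocol 2.5.2). A column of zeros would be noticed, C_min could be recalculated from stored concentrations, and SAP 12 allows undocumented changes to be recorded in the CSR. The point is therefore not critical.

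**A sensible programmer would use post-dose samples.** The objective refers to PK after administration, and an imputed zero is arguably not an observed value. That reading is reasonable. However, SAP 8.2 applies the zero rule expressly to PK parameters and exempts none, and neither document excludes the pre-dose sample. A stated rule gives the wrong result, and the intended reading has to be guessed.

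**A reader might infer that C_min is certain to be 0 in all 48 recipients.** The documents do not support that. It needs a pre-dose result that exists and is BLQ. The PP population in SAP 4.4, used for the parameter summaries, does not require a baseline PK result. No LLOQ or assay background is given, and 48 is a planned, approximate number.

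**A reader might also infer that a post-dose limit cannot repair the definition, or that Cohorts 2 and 5 would be wrongly compared.** The first holds only under assumed PK with a half-life of about 50 days or longer and slow absorption. Protocol 2.5.2 allows for a half-life shorter than those of the comparator antibodies. As for the second, no comparison of C_min between those cohorts is planned.

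**Conclusion.** The point holds in limited form. As written, C_min is 0 for any participant with a BLQ pre-dose sample, expected to be essentially all of the approximately 48 RSM01 recipients. The geometric mean and geometric CV cannot be computed for any group containing a zero, and the CV cannot be computed where all values are zero. This conclusion rests on one assumption, a BLQ pre-dose result, and on no PK model.

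The harm stops at this descriptive secondary endpoint and its exploratory serum counterpart. It does not follow that the PK conclusions of the trial are at risk: C_max, the AUCs, C_D91 and C_D151 are not affected. Severity is moderate to minor.

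The further point, that a simple post-dose limit may fail in Cohort 2, is conditional on assumed PK: half-lives of about 50 days or longer with slow absorption. At 20 to 40 days, Day 151 is the minimum.

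**What to change.** Amend the C_min row in the SAP 8.2 table to the lowest quantifiable concentration observed at or after T_max through Day 151. Leave the existing rule for later BLQ values unchanged, and print beside the summary the number of participants with a BLQ value after T_max. The count is needed because dropping those values pushes the reported minimum upward. Showing late BLQ values as below LLOQ within the summary would conflict with the rule that sets them to missing and would need its own censoring rule, so it is not proposed.

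The alternative is to delete C_min and rely on C_D91 and C_D151. Because C_min is also a protocol endpoint, deletion has to be documented as a change from the protocol.

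The first option costs one table row and one added count; the second costs a short documented change. Neither needs new samples or data. Make the change before unblinding, so that the choice of samples is not a post hoc redefinition.
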